## **10.5 Participant Accrual, Follow-up, and Retention**

The accrual period will be 18 months. The study site will recruit and enroll a total of 16 participants. Each participant will be followed for two weeks following gel administration. Once a participant has enrolled in the study, the study site will make every reasonable effort to retain her for the entire study period.

## **10.6 Data and Safety Monitoring and Analysis**

### **10.6.1 Study Monitoring Committee (SMC)**

No Data and Safety Monitoring Board oversight is planned for this study. The MTN SMC will conduct interim reviews of study progress, including rates of participant accrual, retention, completion of primary and main secondary endpoint assessments, and study or lab issues. These reviews will take place approximately every four to six months, or as needed. At the time of these reviews, or at any other time, the SMC may recommend that the study proceed as designed, proceed with design modifications, or be discontinued.

### **10.6.2 Primary Analysis**

Descriptive statistics to assess women characteristics will be used: for categorical variables, the number and percent in each category; for continuous variables, the mean, median, standard deviation, quartiles and range (minimum, maximum). Similarly, descriptive statistics for continuous variables will be use to describe levels of tenofovir in levels in plasma, in endometrium, in cord blood, in placental tissue, and in amniotic fluid. If a substantial number of women are below the limit of detection of the assay, descriptive statistics for continuous variables will not be used. Rather, proportion of women with detectable levels will be computed along with an exact 95% confidence interval based on the Clopper-Pearson method.

Blood plasma pharmacokinetics of tenofovir will be evaluated after vaginal administration. Pharmacokinetic parameter estimates will include peak concentration ( $C_{max}$ ), time to peak concentration ( $T_{max}$ ), and area under the concentration time curve (AUC) for tenofovir in the blood. Descriptive statistics will be used to summarize these PK parameters in the cohort. Cord blood, amniotic fluid, placental tissue, and endometrial tissue tenofovir levels will also be summarized using descriptive statistics. The ratio of concentrations of tenofovir in maternal blood relative to temporally matched cord blood, amniotic fluid, and endometrial tissue concentrations, and ratio of maternal blood plasma relative to intracellular peripheral blood mononuclear cell (PBMC) tenofovir and tenofovir diphosphate levels will be calculated and summarized using descriptive statistics.

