In addition, oral tenofovir is being studied for use in prevention of peripartum maternal-to-child transmission of HIV-1 in late pregnancy. Data on the first cohort of 15 women enrolled to Pediatric AIDS Clinical Trials Group (PACTG) Protocol 394 have been presented. Women were given an oral dose of 600 mg of tenofovir either at the onset of labor or four hours before scheduled cesarean delivery, and pharmacokinetics and safety in the mother and infant were evaluated. No significant adverse events in the women or infants were attributed to tenofovir. The maternal tenofovir concentrations were similar to those seen after chronic dosing with 300 mg daily in non-pregnant individuals, despite the dose of 600 mg. Median cord blood levels were 76 ng/mL (range 0-309 ng/mL) and the median cord blood/maternal ratio was 0.69. All levels were below the level of quantitation (25 ng/mL) in the infants at 12, 24, and 36 hours of age. The study is continuing with a dose of 900 mg to the mother at onset of labor or before cesarean delivery. Another study, HPTN 057 is also evaluating maternal intrapartum and neonatal pharmacokinetics and safety of tenofovir. Both of these studies are in preparation for a large Phase III trial (expected sample size of approximately 2000 pregnant women) evaluating the use of oral tenofovir with emtricitabine and nevirapine for prevention of perinatal transmission and development of resistance of HIV-1. This selection is based on the expected effectiveness and safety of oral tenofovir in pregnancy. Given the low levels of tenofovir detected in the cord blood after a maternal oral dose of 600 mg, levels after intravaginal exposure to 40 mg would be expected to be lower, but must be evaluated.

Additional safety data regarding the use of tenofovir in pregnancy are available from the Antiretroviral Pregnancy Registry (APR). Through April 1, 2007, 266 cases of first trimester exposure and 208 cases with exposure to tenofovir later in pregnancy have been reported with no increase in birth defects or unusual pattern of defects detected (first trimester: 7 of 266 (2.6%); later in pregnancy: 3 of 208 (1.4%)).

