## 4 STUDY DESIGN

### 4.1 Identification of Study Design

MTN-002 will be a Phase I, single-site, open label investigation into the single-dose pharmacokinetic parameters and placental transfer of tenofovir gel when administered to term gravidas scheduled for elective cesarean section. We will enroll 16 healthy HIV-uninfected women, obtain baseline blood samples, place the gel in the vagina with a target administration time approximately two hours prior to the expected time of cesarean section (optimally a minimum of one hour prior to the collection of cord blood), and then obtain blood samples at the following times: 1, 2, 4, 6, 8, 12 and 24 hours following gel placement. In addition, amniotic fluid, placenta, and endometrial specimens will be collected.

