### **4.5 Study Group**

A single study arm is planned. A total of approximately 16 women will be enrolled. Additional participants will be enrolled to ensure that a total of 16 evaluable participants complete the study.

The following types of participants will be replaced:

- Participants who are enrolled but do not receive study gel
- Participants who receive study gel but whose time of cesarean delivery is greater than 8 hours following the time of study gel administration

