**Table 1: Visit Windows**

Visit	Screening and Enrollment	Gel Administration	0-12 hr PK	24 Hour Evaluation	Two Week Phone Call
Window	Up to four weeks prior to expected date of gel administration (Day 0) and with reasonable allowance for turn-around-time of laboratory analyses drawn at Screening and Enrollment	Up to four hours prior to the expected time of cesarean section, with an optimal minimum of one hour prior to the expected time of cord blood collection	15 minutes +/- scheduled blood draw	22 – 26 hours	Day 10 – Day 18
Target	No target	Defined as Day 0, Time 0  2 hours prior to expected time of cesarean delivery	1, 2, 4, 6, 8, 12 hours following gel placement	24 hours following gel placement	Day 14

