### **7.3 Pharmacokinetic Measures**

For the purposes of scheduling subsequent evaluation and follow-up, the date of gel administration will be considered Day 0. The time of gel administration will be considered Time 0. Timed pharmacokinetic measures are timed by hours passed since gel administration, not cesarean section.

A physician investigator will not be the primary or first assistant surgeon for the cesarean section. A physician investigator will be responsible for collection of study-related specimens in the operating room.

Flow cytometry for CD38 and CD95 will be obtained pre-dose on Day 0. This will be required as a surrogate for cell activation and proliferation markers, respectively, to serve as covariates in the intracellular model building.

If not already in place, a saline lock (or similar device) will be inserted to facilitate the collection of multiple blood specimens. This device may be replaced as needed in the event of a non-functioning device. Specimens will not be drawn from the site of an ongoing intravenous infusion.

Surgery and anesthesia may contribute to a temporary increase in intravascular volume, though this is often a function of the duration of surgery. Accordingly, there may be an increase in volume of distribution, especially for water soluble drugs, that would transiently reduce drug concentrations in the blood. Drugs used in anesthesia (including their time of administration) and operative time are routinely recorded and these data will be captured.

As the majority of these evaluations are likely to occur in the pre-operative area, operating room, and post-operative areas of the hospital, participants will not receive reimbursement for this study visit in these settings, which are expected to be relatively short-term. Rather, reimbursement will be provided for all study participation that occurs in the inpatient setting at the 24 Hour Evaluation or other setting as needed.

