**Table 3: Pharmacokinetic Measures: Gel Administration Day (Day 0)**

Pharmacokinetic Measures		
Component	Procedure/Analysis	
Pre-Gel	Admin.	
 
• Update locator information
 
• Place copy of consent in inpatient chart
 
• Review inpatient chart
 
• Administer eligibility assessment/Confirm eligibility
 
• Schedule next study evaluation
 

	Clinical	
 
• Update medical history
 
• Update concomitant medications
 
• Update adverse events
 
• Perform targeted physical exam
 
• Perform pelvic exam
 

	Lab	
 
• Insert/Replace saline lock or similar (if not already inserted)
 
• Draw blood for:               
 
○ maternal plasma tenofovir level
 
○ flow cytometry
 
 
 

Gel	
 
• Gel administration by study physician
 
	
Post-Gel	C/S	
 
• Amniotic fluid collection
 
• Endometrial tissue collection
 

	Clinical	
 
• Collect adverse events at each PK time point
 
• Review inpatient chart (during 1-12 hours post-gel)
 

	Lab	
 
• Insert/Replace saline lock as needed
 
• Draw blood for maternal plasma tenofovir level               
 
○ 1, 2, 4, 6, 8, and 12 hour time points                   
 
▪ Note: the above time points are after gel administration.
 
▪ Some time points may occur before cesarean section.
 
▪ The allowable window for each blood draw is +/-15 minutes.
 
 
 
 
 
• Cord blood collection               
 
○ may also be collected during cesarean section if possible
 
 
 
• Placental tissue collection               
 
○ may also be collected during cesarean section if possible
 
 
 

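### The transfer ratios in Section 10.6.2 require a time-matched maternal level, but no maternal draw is tied to delivery, and the ratio as worded drops every woman with no detected transfer.

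*Protocol*

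**What the plan says.** Section 10.6.2 lists among the planned summaries "The ratio of concentrations of tenofovir in maternal blood relative to temporally matched cord blood, amniotic fluid, and endometrial tissue concentrations". The natural reading puts maternal blood in the numerator and the cord, fluid or tissue level in the denominator. Placental tissue is not in that list, although Sections 4.2 and 10.2 name it as a placental-transfer endpoint.

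On maternal sampling, Section 4.1 says staff will "obtain blood samples at the following times: 1, 2, 4, 6, 8, 12 and 24 hours following gel placement". Section 7.3 adds: "Timed pharmacokinetic measures are timed by hours passed since gel administration, not cesarean section". Table 3 states that "The allowable window for each blood draw is +/-15 minutes". Neither Table 3 nor the schedule in Appendix I has a maternal draw at delivery. Appendix I places amniotic fluid and endometrial collection during the cesarean section, and cord blood and placental collection during or after it.

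On the interval from gel to delivery, the Table 1 target is "2 hours prior to expected time of cesarean delivery" and its window is "Up to four hours prior to the expected time of cesarean section". Section 4.6 accepts that surgery times may change. Section 4.5 replaces only "Participants who receive study gel but whose time of cesarean delivery is greater than 8 hours following the time of study gel administration", so women delivering up to 8 h after gel are kept.

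For the oral-dose study cited in Section 2.4, the protocol reports that "the median cord blood/maternal ratio was 0.69", which is the opposite direction from Section 10.6.2.

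**The concern.** A transfer ratio is interpretable only if both levels refer to about the same moment. The protocol asks for such matching, but the schedule supplies it only when delivery happens to coincide with a draw. Section 7.3 itself warns that surgery and anesthesia may temporarily lower blood concentrations, so a draw taken before the operation may not represent the level at delivery.

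Direction matters separately. With the cord, fluid or tissue level underneath, a woman with quantifiable plasma and nothing detected on the other side has no finite ratio. A descriptive summary of the finite values would then describe only women in whom transfer was detected. The fallback to detection proportions in Section 10.6.2 is written for levels; the sentence on ratios carries no such exception.

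**Working it through.** The plan attaches no figure to the ratios, so there is none to reproduce. The check uses the plan's own schedule and planning rate.

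**Timing**

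Inputs: maternal draws at 1, 2, 4, 6, 8, 12 and 24 h (Section 4.1); window of 15 minutes, or 0.25 h, either side (Table 3); target delivery 2 h after gel (Table 1); women kept up to 8 h (Section 4.5).

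Gap = distance from the delivery time to the nearest scheduled draw.

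- Delivery at 2 h: gap 0.
- Delivery at 1.5, 2.5 or 3.5 h: gap 0.5 h.
- Delivery at 3, 5 or 7 h, midway between draws 2 h apart: gap 1.0 h. This is the maximum for any delivery from 1 to 8 h.
- If both bracketing draws drift away from delivery by the full window: 1.0 + 0.25 = 1.25 h.

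The documents give no distribution of delivery times. As an illustration only, suppose deliveries are spread evenly over 1 to 4 h after gel.

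- More than 0.25 h from a nominal draw: 1.25–1.75 h and 2.25–3.75 h, so (0.5 + 1.5)/3 = 67%.
- More than 0.5 h from a nominal draw: 2.5–3.5 h, so 1.0/3 = 33%.

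If most deliveries fall close to 2 h, both shares are smaller.

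**Finite ratios as worded**

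Inputs: N = 16 and a true detection rate of 5% in endometrium, cord blood, placental tissue and amniotic fluid (Section 10.4).

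The number of women with a detectable denominator is Binomial(16, 0.05).

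- Expected number: 16 × 0.05 = 0.8 per matrix.
- Probability of none: 0.95^16 = 0.44.
- Probability of one or none: 0.44 + 16 × 0.05 × 0.95^15 = 0.81.
- At a rate of 25%, the level Section 10.4 aims to exclude, the expected number is still only 16 × 0.25 = 4.

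**What turning the ratio over changes**

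Let the cord, fluid or tissue level be below its limit of quantitation (LLOQ) while maternal plasma is quantifiable. Cord over maternal is then less than LLOQ/maternal, a bound near zero when plasma is well above the limit. Maternal over cord is greater than maternal/LLOQ, with no upper limit.

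The two statements carry the same information, but Section 10.6.2 provides for neither. The number of women with both levels quantifiable is the same in either direction: at most 0.8 expected per matrix at the 5% rate.

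**The case against.** The strongest reply is that little depends on these ratios. Sections 4.2 and 10.2 define placental transfer by levels, Section 10.4 is built on detection proportions, and Section 10.6.2 reports those with exact intervals when many values are below the limit. No listed endpoint fails if the ratios are sparse. That stands, and it limits the weight of this point. It is also true that the 2 h target coincides with a draw, that 5% is a planning assumption which the more sensitive assay in Section 2.10 might overturn, and that rules for values below the limit may sit in an analysis plan that is not shown. An analysis plan cannot, however, supply a delivery sample that was never drawn, and the ratio's direction and the absence of placental tissue are fixed in this protocol.

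Three stronger readings are tempting, and the documents support none of them.

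- A reader might infer that turning the ratio over gives a usable value in the 33% of women expected to have detectable plasma (Section 10.3). The detection that Section 2.10 describes for the earlier gel study is at any point in the 12 hours after dosing, not at delivery. Many of those women would also yield only a bound.
- A reader might infer that a 1 h gap typically shifts the ratio about 1.5-fold, from the fall from 25.8 to 10.9 ng/mL between 2 and 4 h in Section 2.10. That is one woman whom the protocol calls an outlier; the next highest peak was 7.1 ng/mL.
- A reader might infer that results could not be set beside the quoted 0.69. A median can be inverted (1/0.69 = 1.45). What inversion cannot restore is the pairs already dropped. The oral study's cord levels ran from 0 (Section 2.4), and a zero has no finite value on the Section 10.6.2 scale.

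**Conclusion.** The point holds as a moderate defect in a supplementary descriptive summary. The matching that Section 10.6.2 requires is not guaranteed by the schedule: the gap is nil on target, at most 1 h between draws for deliveries from 1 to 8 h, and at most 1.25 h with the window. The effect of that gap on the ratio cannot be sized from the documents.

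As worded, the ratio is expected to be finite in 0.8 of 16 women per matrix, and only where transfer was detected. This rests on the 5% planning rate and on reading the phrase as maternal over the other matrix. A higher detection rate would ease the sparsity, but women with no detected transfer would still drop out. The omission of placental tissue rests on no assumption.

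**What to change.** - **Sampling (Section 7.3, Table 3, Appendix I):** add one maternal plasma sample at cord clamping, from the saline lock already planned, and record the clamp time. Section 7.3 bars draws from the site of a running infusion, so the lock has to be separate from it.
- **If that sample is missing:** use the nearest scheduled draw and report the time gap. Interpolate only when both bracketing draws are quantifiable.
- **Ratios (Section 10.6.2):** define them as cord blood, amniotic fluid, placental tissue and endometrial tissue, each divided by maternal plasma.
- **Values below the limit:** when the numerator is below its limit and maternal plasma is quantifiable, report the upper bound LLOQ/maternal, using the limit for that matrix. Section 7.9.2 notes that the tissue and amniotic fluid assays are still to be developed, so those limits must be stated once set.

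The cost is one small extra blood sample, one recorded time and a few lines of text. The sample has to be planned before enrolment because it cannot be recovered afterwards. The gain is correct timing and the retention of non-transfer pairs as bounds, not more women with both levels quantifiable.

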## **11 DATA HANDLING AND RECORDKEEPING**

### **11.1 Data Management Responsibilities**

Study case report forms will be developed by the SDMC. Quality control reports and queries routinely will be generated and distributed by the SDMC to the study site for verification and resolution.

### **11.2 Source Documents and Access to Source Data/Documents**

Source documents and access to source data/documents will be maintained in accordance with the Requirements for Source Documentation in DAIDS Funded and/or Sponsored Clinical Trials. The investigator will maintain, and store securely, complete, accurate and current study records throughout the study. In accordance with U.S. regulations, the investigator will retain all study records on site for at least two years after study closure. Study records will not be destroyed prior to receiving approval for record destruction from DAIDS. Applicable records include source documents, site registration documents and reports, correspondence, informed consent forms, and notations of all contacts with the participant.

### **11.3 Quality Control and Quality Assurance**

Quality control and quality assurance procedures for MTN-002 will be performed in accordance with Requirements for Clinical Quality Management Plans at DAIDS Funded and/or Supported Clinical Research Sites.

### **11.4 Study Coordination**

DAIDS holds the IND application for this study (#55690). Assignment of all sponsor responsibilities for this study will be specified in a Clinical Trials Agreement executed by DAIDS and CONRAD. Training and written instructions outlining management and reporting, study gel dispensing, product accountability, and other study operations will be provided by Family Health International, the Statistical Center for HIV/AIDS Research & Prevention (SCHARP), and the MTN Network Laboratory.

## **12 CLINICAL SITE MONITORING**

Study monitoring will be carried out by PPD (Wilmington, NC). On-site study monitoring will be performed in accordance with Requirements for On-Site Monitoring of DAIDS Funded and/or Sponsored Clinical Trials. Site monitoring visits will be conducted to assess compliance with Health and Human Services (HHS) Regulations 45 Code of Federal Regulations (CFR) Part 46 and 21 CFR Parts 50, 56, and 312. Study monitors will visit the site to:

- Verify compliance with human subjects and other research regulations and guidelines, including confidentiality procedures, informed consent process, and regulatory documentation
- Assess adherence to the study protocol, site SOPs, and local counseling practices
- Confirm the quality and accuracy of information collected at the study site and entered into the study database, including the validation of data reported on case report and DataFax forms
- Assess the resolution of any past or ongoing issues identified at previous monitoring visits

Site investigators will allow study monitors to inspect study facilities and documentation (e.g., informed consent forms, clinic and laboratory records, other source documents, case report forms), as well as observe the performance of study procedures. Investigators also will allow inspection of all study-related documentation by authorized representatives of the MTN CORE, MTN Network Laboratory, Family Health International, SCHARP, NIAID, and US regulatory authorities. A site visit log will be maintained at the study site to document all visits.

## **13 HUMAN SUBJECTS PROTECTIONS**

The investigators will make efforts to minimize risks to human participants. Participants and study staff members will take part in a thorough informed consent process. Before beginning the study, the investigators will have obtained IRB approval and the protocol will have been reviewed by the FDA. The investigators will permit audits by the NIH, CONRAD, the FDA, or any of their appointed agents.

### **13.1 Institutional Review Board**

The participating institution is responsible for assuring that this protocol and the associated informed consent documents and study-related documents are reviewed and approved by the Institutional Review Board (IRB) prior to implementation of the protocol. Any amendments to the protocol and/or informed consents must be approved by the IRB and DAIDS prior to implementation.

### **13.2 Protocol Registration**

The study site will complete protocol registration with the DAIDS RCC Protocol Registration Office. For additional information, refer to the protocol registration documents located at <http://rcc.tech-res.com/forms.htm>. Protocol registration must

occur as a condition for site-specific study activation; no participants may be screened or enrolled in this study prior to obtaining protocol registration approval and completing all other study activation requirements. Protocol registration material can be sent electronically to [[contact]](mailto:[contact]). For questions regarding protocol registration, please call [contact]. MTN CORE (FHI) staff will notify the study site when all activation requirements have been met by issuing a site-specific study activation notice. Study implementation may not be initiated until the activation notice is issued.

The study will be conducted in full compliance with the protocol. The protocol will not be amended without prior written approval by the Protocol Chair and NIAID Medical Officer. All protocol amendments must be submitted to and approved by the IRB and the RCC prior to implementing the amendment.

